### 12.3.3. Adverse Events of Special Interest

Adverse events of special interest will include: infusion reactions (IRs), anaphylaxis, gout flares, and cardiovascular events. An external adjudication committee will adjudicate the AESIs of IR, anaphylaxis and cardiovascular events.

#### 12.3.3.1. *Infusion Reactions (IRs) and Anaphylaxis*

An IR will be defined as any infusion-related AE or cluster of temporally-related AEs, not attributable to another cause, which occur during the pegloticase infusion and for up to 2 hours post infusion. Other AEs that occur outside of the 2-hour window following the infusion may also be categorized as an IR at the PI's

This document is confidential.

discretion. Signs and symptoms of the IR and treatments administered will be documented in the medical record and in the eCRF, and will be adjudicated.

Examples of AEs not considered possible IRs include, but are not limited to: laboratory abnormalities that are unlikely to have occurred during or within 2 hours following the infusion (e.g., anemia), gout flares, most infectious diseases, or the recurrence or worsening of a known chronic medical problem identified in the subject's medical history.

The signs and symptoms associated with each event are entered on the eCRF and will be coded with the MedDRA dictionary.

Any incidence of anaphylaxis should be reported as an SAE. Anaphylaxis will be defined using the National Institute of Allergy and Infectious Diseases/Food Allergy and Anaphylaxis Network (NIAID/FAAN) criteria [Sampson et al, 2006] , and will be adjudicated:

1. Acute onset of an illness (minutes to several hours) with involvement of the skin, mucosal tissue, or both (e.g., generalized hives; pruritus or flushing; urticaria, and angioedema (of lips, tongue, or uvula) and  $\geq 1$  of the following:
  - a. Respiratory compromise (e.g., dyspnea, wheeze-bronchospasm, stridor, reduced peak expiratory flow, hypoxemia); and
  - b. Reduced blood pressure or associated symptoms of end-organ dysfunction (e.g., hypotonia [collapse], syncope, incontinence).
2. Two or more of the following that occur rapidly after exposure to a likely allergen for that subject (minutes to several hours):
  - a. Involvement of the skin-mucosal tissue (e.g., generalized hives, itch-flush, swollen lips-tongue, uvula);
  - b. Respiratory compromise (e.g., dyspnea, wheeze-bronchospasm, stridor, reduced peak expiratory flow, hypoxemia);
  - c. Reduced blood pressure or associated symptoms (e.g., hypotonia [collapse], syncope, incontinence); and
  - d. Persistent gastrointestinal symptoms (e.g., crampy, abdominal pain, vomiting).
3. Reduced blood pressure after exposure to known allergen for that subject (minutes to several hours): systolic blood pressure  $<90$  mmHg or  $>30\%$  decrease from that subject's baseline.

The signs and symptoms associated with each event are entered on the eCRF and will be coded to the MedDRA dictionary.

Summaries of IRs and anaphylaxis will group events by 3 categories:

- Anaphylaxis
- Infusion reactions including anaphylaxis
- Infusion reactions excluding anaphylaxis

Both the investigator-reported and adjudicated events and the associated signs and symptoms, will be summarized separately by SOC, PT, severity, and the time relative to the most recent pegloticase infusion for each category above.

Time relative to the most recent pegloticase infusion will be categorized as: during infusion,  $\leq 2$  hours after infusion,  $> 2$  hours to 24 hours after infusion, and  $> 24$  hours after infusion. If the time of the infusion reaction or anaphylaxis is missing, the category will be assigned as "Missing".

This document is confidential.

Serious events and the associated symptoms will be summarized by SOC and PT for each category.

The number of events per subject, the number of events and serious events per infusion, and the number of subjects with the first event by infusion number will be summarized as well for each category. IRs (including anaphylaxis) that occur on the same date will be considered one event.

Time to first infusion reaction or anaphylaxis (Kaplan-Meier analysis) will be plotted. Time to first infusion reaction or anaphylaxis for subjects who experience infusion reaction or anaphylaxis (continuous variable descriptive stats) will be summarized. Summaries of events will be tabulated only if 5 or more subjects have either an event adjudicated as an IR or anaphylaxis or any events in the database identified as IRs or anaphylaxis.

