### 9.6.7 Safety Analysis

Treatment-emergent AEs are defined as events with an onset date on or after the start of the first pegloticase infusion through 30 days after the last dose of pegloticase. AEs that occur more than 30 days after the last dose of pegloticase through the 3-month follow-up visit will also be summarized.

The number and percentage of subjects experiencing AEs will be summarized by system organ class and preferred term. Summaries by maximum severity and relationship to study drug will also be provided. SAEs and AEs leading to discontinuation of study drug will be presented by system organ class and preferred term. The proportion of subjects with each AESI will also be summarized.

Laboratory test results will be summarized by study visit and change from baseline. Shift tables for laboratory parameters by Common Terminology Criteria for Adverse Events grade will be presented. Laboratory test results will also be classified relative to the normal reference range (normal, low, or high).

Vital signs, including BP, respiratory rate, temperature, and heart rate, will be summarized by study visit and change from baseline.

Prior and concomitant medications will be summarized and/or included in the data listings.

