**5.5. Safety and Tolerability Endpoints**

Safety and tolerability endpoints are:

- Overall AE/SAE profile;
  - Incidences of AESI: IRs, anaphylaxis, gout flares, cardiovascular events;
- Laboratory tests: change from baseline to each scheduled assessment;
- Electrocardiogram (ECG)
- Vital signs: change from baseline to each scheduled assessment and physical examination; and
- Incidence of renal rejection (biopsy proven).

This document is confidential.

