### 12.3.2. Presentation of Results

All AEs, both serious and non-serious, will be assessed for severity using the Rheumatology Common Toxicity Criteria (CTC) v2.0. Summaries of TEAEs will be for the safety population.

An overall summary of TEAEs will be provided, including the number and percentage of subjects with each AE type as well as the number of events for each of the following:

- TEAEs
- Serious TEAEs
- TEAEs related to pegloticase
- Serious TEAEs related to pegloticase
- TEAEs with a Rheumatology CTC Criteria of 3 or higher
- TEAEs leading to permanent withdrawal of pegloticase
- TEAEs related to pegloticase leading to permanent withdrawal of pegloticase
- TEAEs leading to death
- TEAEs of special interest

Using the safety population, an overall summary of AEs occurring during the follow-up period (with onset more than 30 days after the last dose of study medication), including the number and percentage of subjects with each AE type as well as the number of events for each of the following:

- AEs
- Serious AEs
- AEs with a Rheumatology CTC Criteria of 3 or higher
- AEs leading to death
- AEs of special interest

This document is confidential.

Percentages for the overall summary of AEs during follow-up will be based on the number of subjects who had follow-up more than 30 days after last dose of medication.

Additional AE summaries will be provided by onset period, including the number, percentage of subjects, experiencing TEAEs for the following:

- TEAEs overall and by SOC and PT for the: Pegloticase Treatment Period and Follow-up Period
- TEAEs by maximum severity, overall and by SOC and PT for the Pegloticase Treatment Period
- TEAEs related to pegloticase overall and by SOC and PT for the Pegloticase Treatment Period
- TEAEs related to pegloticase by maximum severity, overall and by SOC and PT for the Pegloticase Treatment Period
- Serious TEAEs, overall and by SOC and PT for the: Pegloticase Treatment Period and Follow-up Period
- TEAEs leading to permanent withdrawal of pegloticase, overall and by SOC and PT for the Pegloticase Treatment Period

The incidence per person years of exposure to pegloticase will be provided on all tables except those summarizing events by maximum intensity, and those for the post-treatment follow-up period.

Person years of exposure to pegloticase is defined as  $[(\text{last treatment date in the period} - \text{first treatment date in the period} + 1)/365.25]$ .

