For summaries by SOC, PT, and maximum severity, a subject will only be counted once for each SOC based on the maximum intensity level reported for that SOC and once for each unique PT within that SOC level at the maximum intensity level reported for that PT. For summaries by SOC and PT only, a subject will be counted at most once at the SOC level and at most once at each unique PT within the SOC level. Summaries presenting the frequency of TEAEs by SOC and PT will be ordered alphabetically by SOC and then, within a SOC, alphabetically by PT.

In addition to the listing of all AEs, separate listings will be provided for serious AEs, AEs leading to withdrawal of pegloticase, AEs leading to study discontinuation, AEs of special interest, and AEs leading to death. TEAEs and the period of onset will be identified on each listing. A listing of any subject with an interruption in treatment of pegloticase due to COVID-19 will be created which will identify AEs as pre-interruption, during interruption, or post-interruption.

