#### 12.3.3.2. *Cardiovascular Events*

Cardiovascular events will include Major Adverse Cardiovascular Events (MACE).

Any MACE including Non-fatal myocardial infarction, non-fatal stroke, cardiovascular death, and congestive heart failure.

- For cardiovascular death:
  - Standardized MedDRA Queries (SMQ): Myocardial infarction, Ischaemic Central Nervous System (CNS) Vascular conditions; Haemorrhagic central nervous system vascular conditions, Central nervous system vascular disorders, not specified as haemorrhagic or ischaemic, Embolic and thrombotic events (arterial, venous, vessel type unspecified and mixed arterial and venous), Cardiac failure, shock-associated conditions, Torsade de pointes/QT prolongation, Arrhythmia related investigations, signs and symptoms, Cardiomyopathy, Supraventricular tachyarrhythmias (narrow), Ventricular tachyarrhythmias (narrow), Conduction defects
  - All PTs under SOC of Cardiac disorders
  - HLGT Aneurysm
- For non-fatal myocardial infarction: SMQ Myocardial infarction
- For non-fatal stroke: SMQ: Ischaemic Central Nervous System (CNS) Vascular conditions; Haemorrhagic central nervous system vascular conditions; Central nervous system vascular disorders, not specified as haemorrhagic or ischaemic
- Congestive heart failure: SMQ Cardiac failure

Cardiovascular events will be tabulated only if 5 or more subjects have experienced a cardiovascular event or have an event adjudicated as a cardiovascular event. Using the safety population, cardiovascular events will be summarized by MedDRA SOC and PT, adjudicated as well as any identified by investigator.

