#### **14. Changes from Analysis Planned in Protocol**

The analysis population definitions have been changed:

- Per the protocol, only the modified Intent-to-Treat (mITT) population was defined as all subjects who receive at least 1 dose of pegloticase. The mITT population was planned to be used for analysis of ADA, efficacy and safety data.
- For the purposes of ease of future integration with other pegloticase studies, the mITT definition has been removed, and instead has been replaced by the Intent-To-Treat (ITT) population definition (for the analysis of ADA and efficacy data) and the safety population definition (for the analysis of safety data). Both the ITT and the safety population are defined as all subjects who receive at least 1 dose of pegloticase.

The phrasing of the safety endpoints relating to laboratory tests and vital signs has been updated from "Laboratory tests" and "Vital signs" to "Laboratory tests: change from baseline to each scheduled assessment" and "Vital signs: change from baseline to each scheduled assessment," respectively.

This document is confidential.

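### The SAP tabulates infusion reactions, anaphylaxis and cardiovascular events only if 5 or more subjects (25% of 20) are affected, although the protocol promises each AESI proportion without a minimum count

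*SAP*

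**What the plan says.** Protocol 9.6.7 (Safety Analysis) states: "The proportion of subjects with each AESI will also be summarized". No minimum count is attached. SAP 5.5 carries the same endpoint forward, again unconditionally: "Incidences of AESI: IRs, anaphylaxis, gout flares, cardiovascular events".

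SAP 12.3.3 then sets out the AESI analyses. For IRs and anaphylaxis (12.3.3.1), summaries are tabulated "only if 5 or more subjects have either an event adjudicated as an IR or anaphylaxis or any events in the database" flagged as IRs or anaphylaxis. For the cardiovascular AESI (12.3.3.2): "Cardiovascular events will be tabulated only if 5 or more subjects have experienced a cardiovascular event or have an event adjudicated" as one. Gout flares, the fourth AESI, are summarised in 12.3.3.3 with no such condition.

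SAP section 14 lists the departures from the protocol. It covers the renamed analysis populations and goes as far as noting that "The phrasing of the safety endpoints relating to laboratory tests and vital signs has been updated". The 5-subject condition is not mentioned. Neither document says why 5 was chosen.

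Some outputs do not depend on the count. SAP 12.3.2 has an overview row, "TEAEs of special interest", and tables of all and serious treatment-emergent events by coded term. It also says that "separate listings will be provided for serious AEs, AEs leading to withdrawal of pegloticase, AEs leading to study discontinuation, AEs of special interest".

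**The concern.** The condition makes the reporting of a named safety endpoint depend on its own result. With 1 to 4 affected subjects out of 20, which is 5% to 20%, the IR, anaphylaxis or cardiovascular proportion gets no table of its own. A reader would have to rebuild it from listings and coded terms.

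That is awkward for two reasons. IR risk is part of the rationale for the study: Protocol 7.2 expects immunosuppression to lower it and wants to support the use of the serum urate stopping rule for the same purpose. A low rate in one arm could not separate those two explanations, but neither can be discussed without the number. In addition, an external committee adjudicates IRs, anaphylaxis and cardiovascular events, and below 5 subjects the SAP text specifies no table of its conclusions.

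**Working it through.** **Inputs**
- Planned N = 20 (Protocol 9.6.9). COVID-19 replacement may raise it (Protocol 9.3.4.1); 22 and 24 are taken as assumed values.
- Threshold: 5 subjects (SAP 12.3.3.1 and 12.3.3.2). There is no derivation to reproduce. 5/20 = 25%; 5/22 = 22.7%; 5/24 = 20.8%.
- IR rate in Phase 3, every-2-week arm: 22/85 = 25.9%, matching the stated 26% (Protocol 7.1.2).
- IR rate with a two-consecutive-values stopping rule: 8%, from a post-hoc analysis (Protocol 7.1.2). This study uses such a rule.
- Cardiovascular event rate: no expected rate is given. Assumed 5%, 10% and 20%.

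**Formula.** If X is the number of affected subjects, X ~ Binomial(N, p). The table is withheld when X ≤ 4, with probability P(X ≤ 4) = Σ C(N,k) p^k (1−p)^(N−k), k = 0 to 4.

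**IR at p = 0.08, N = 20.** P(0) = 0.92^20 = 0.1887. The terms for k = 1, 2, 3, 4 are 0.3282, 0.2711, 0.1414 and 0.0523, which sum to 0.7930. So P(X ≤ 4) = 0.1887 + 0.7930 = 0.9817.

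| Event | Rate | Withheld, P(X ≤ 4) | of which 1 to 4 affected |
|---|---|---|---|
| IR/anaphylaxis | 8% (with stopping rule) | 98.2% | 79.3% |
| IR/anaphylaxis | 26% (Phase 3) | 37.5% | 37.3% |
| Cardiovascular | 5% (assumed) | 99.7% | 63.9% |
| Cardiovascular | 10% (assumed) | 95.7% | 83.5% |
| Cardiovascular | 20% (assumed) | 63.0% | 61.8% |

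**Sensitivity to N at 8%.** P(X ≤ 4) is 98.8% for N = 18, 97.3% for N = 22 and 96.1% for N = 24. A few replacements do not change the picture.

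**What a short table would show.** Exact (Clopper-Pearson) 95% limits for the counts now withheld, out of 20:

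| Count | Proportion | 95% CI |
|---|---|---|
| 0 | 0% | 0 to 16.8% |
| 1 | 5% | 0.1 to 24.9% |
| 2 | 10% | 1.2 to 31.7% |
| 3 | 15% | 3.2 to 37.9% |
| 4 | 20% | 5.7 to 43.7% |

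**What is left below 5 subjects.**
- The AESI overview row is not stated to be split by type, so it would pool these events with gout flares, which the SAP describes as common with potent urate-lowering drugs.
- The coded-term tables do not reproduce the AESI categories. An IR can be a cluster of AEs, and the cardiovascular category is assembled from several MedDRA queries.
- Anaphylaxis should appear among the serious events ("Any incidence of anaphylaxis should be reported as an SAE"), but not with its adjudicated status, and non-serious IRs would not be there.
- The AESI listing contains the events but no proportion.
- The Kaplan-Meier plot of time to first IR or anaphylaxis may survive, because only tabulation is made conditional.

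**The case against.** The best counter-argument is about scope. In 12.3.3.1 the condition follows a run of detailed breakdowns (coded term, severity, timing, per infusion) and could be meant to govern only those. SAP 5.5 keeps the incidences and section 14 withdraws nothing, which would fit. On that reading the wording is ambiguous but no endpoint has been dropped. This does not work for 12.3.3.2, where the condition applies flatly to tabulating cardiovascular events at all. In 12.3.3.1 nothing outside the condition is specified to supply the simple proportion.

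Several other points stand:
- The SAP's index of tables (section 18) is not in the text supplied, so a per-AESI row in the overview cannot be excluded.
- Nothing is hidden. With 20 subjects and at most 4 cases, a reader with the listing can count.
- The IR condition pools IRs with anaphylaxis and counts either adjudicated or otherwise identified cases. It is therefore easier to meet than a condition on any one definition.
- The 8% is a post-hoc figure from trials that excluded transplant recipients. At 26% the tables would appear 62.5% of the time.
- The 98.2% includes 18.9 percentage points with no events, where only a zero row is lost.
- Protocol 7.1.2 mentions one myocardial infarction among 7 kidney transplant recipients in an earlier pegloticase trial. One case is too few to serve as a rate. Taken at face value, 1/7 gives P(X ≤ 4) of about 85%, inside the range shown.
- Protocol 9.6.7 does not itself ask for investigator-reported and adjudicated proportions separately. That split is the SAP's own, in 12.3.3.1 and 12.3.3.2.

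**Conclusion.** The concern holds. As written, the SAP makes the tabulation of two AESI groups depend on at least 25% of subjects being affected. The protocol sets no such condition, and section 14 does not declare the departure. At the IR rate the protocol itself cites for a stopping rule, withholding is the expected outcome, and about four times in five (79.3%) it would happen with 1 to 4 subjects affected.

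These probabilities assume independent subjects, a common rate and N near 20; the cardiovascular figures rest on assumed rates. No estimate, test or data collection is invalidated, and the events remain in other outputs. The SAP should be corrected, but the validity of the trial is not at stake. The main uncertainty is the index of tables: if it already contains an unconditional row for each AESI, the remaining need is to say so in the body of the SAP.

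**What to change.** Limit the 5-subject condition in SAP 12.3.3.1 and 12.3.3.2 to the detailed breakdowns (coded term, severity, timing, per infusion), where sparse cells justify it.

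At any count, including zero, tabulate n/N (%) for:
- IRs including anaphylaxis;
- IRs excluding anaphylaxis;
- anaphylaxis;
- cardiovascular events, including MACE.

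Give each as investigator-reported and as adjudicated. An exact 95% CI could be added, using the Clopper-Pearson method the SAP already applies to responders. State whether the Kaplan-Meier plot falls under the condition.

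If the sponsor prefers to keep the condition on the proportions themselves, section 14 should declare it as a change from Protocol 9.6.7.

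The cost is a few lines of SAP wording and one short table from data already being collected and adjudicated.

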#### 12.3.3.2. *Cardiovascular Events*

Cardiovascular events will include Major Adverse Cardiovascular Events (MACE).

Any MACE including Non-fatal myocardial infarction, non-fatal stroke, cardiovascular death, and congestive heart failure.

- For cardiovascular death:
  - Standardized MedDRA Queries (SMQ): Myocardial infarction, Ischaemic Central Nervous System (CNS) Vascular conditions; Haemorrhagic central nervous system vascular conditions, Central nervous system vascular disorders, not specified as haemorrhagic or ischaemic, Embolic and thrombotic events (arterial, venous, vessel type unspecified and mixed arterial and venous), Cardiac failure, shock-associated conditions, Torsade de pointes/QT prolongation, Arrhythmia related investigations, signs and symptoms, Cardiomyopathy, Supraventricular tachyarrhythmias (narrow), Ventricular tachyarrhythmias (narrow), Conduction defects
  - All PTs under SOC of Cardiac disorders
  - HLGT Aneurysm
- For non-fatal myocardial infarction: SMQ Myocardial infarction
- For non-fatal stroke: SMQ: Ischaemic Central Nervous System (CNS) Vascular conditions; Haemorrhagic central nervous system vascular conditions; Central nervous system vascular disorders, not specified as haemorrhagic or ischaemic
- Congestive heart failure: SMQ Cardiac failure

Cardiovascular events will be tabulated only if 5 or more subjects have experienced a cardiovascular event or have an event adjudicated as a cardiovascular event. Using the safety population, cardiovascular events will be summarized by MedDRA SOC and PT, adjudicated as well as any identified by investigator.

#### 12.3.3.3. *Gout Flares*

It is common for potent ULTs to lead to acute attacks of gout. Gout flares will be confirmed through questioning the subject or direct observation by the Investigator and will be recorded as AEs.

The number of gout flares (recorded in the AE eCRF) per subject will be summarized using the safety population. These events will be further summarized by month of occurrence. A month is defined as 30 days. Events are summarized for each month according to the onset date of the flares, and only summarized in the month of onset. For month 1, percentages will be based on the number of subjects in

This document is confidential.

the safety population. For the other months of the pegloticase treatment period, percentages will be based on the number of subjects who had follow-up at least through the start of the period-specific time period. Subject self-reported gout flare assessment will also be summarized. The 30 days following the end of treatment are included in the follow-up time period.

Percentages will be calculated using the number of subjects in the safety population having follow-up through the beginning of the respective month.

#### **12.4. Laboratory Evaluations**

Blood (for hematology and clinical chemistry) will be collected at Screening, prior to the pegloticase infusion on Day 1 and at the Week 2, 6, 14, and 22 Visits, the End of Pegloticase Infusions Visit (if applicable), the Week 24/End of Study/Early Termination Visit and 3 month Post Treatment Follow up Visit.

Urine (for albumin:creatinine ratio) samples will be collected at Screening, prior to the pegloticase infusion on Day 1 and at the Week 6, 14, and 22 Visits, the End of Pegloticase Infusions Visit (if applicable) and Week 24/End of Study/Early Termination Visit.

Urine (for human chorionic gonadotropin) samples will be collected at selected visits.

Safety laboratory assessments will include:

- Hematology: complete blood count with differential (hemoglobin concentration, hematocrit, erythrocyte count, platelet count, leukocyte count, and differential leukocyte count);
- Chemistry: albumin, transaminases (aspartate aminotransferase, alanine aminotransferase), alkaline phosphatase, total bilirubin, creatinine (including calculation for eGFR calculated by the Modification of Diet in Renal Disease [MDRD] study equation :  $175 \times (S_{cr[mg/dL]})^{-1.154} \times (age)^{-0.203} \times (0.742 \text{ if female}) \times (1.212 \text{ if African American})$  or  $175 \times (S_{cr[\mu mol/L]}/88.4)^{-1.154} \times (age)^{-0.203} \times (0.742 \text{ if female}) \times (1.212 \text{ if African American})$ ), glucose, sodium, potassium, calcium, chloride, total protein, blood urea nitrogen, and human chorionic gonadotropin (at the Screening Visit and the Week 24/End-of-Study/Early Termination Visit for all female subjects of childbearing potential); and
- Urine: albumin:creatinine ratio, and human chorionic gonadotropin (for all female subjects of childbearing potential).

A central study laboratory will be used for all protocol-specified clinical laboratory parameters.

Laboratory results will be displayed using the conventional units. for all summaries and listings. Clinical laboratory test results (hematology and chemistry) and their changes from baseline will be summarized by visit for the safety population using descriptive statistics by pegloticase treatment status (On Treatment, Post-Treatment, and Overall).

If a continuous laboratory value is reported as either below or above the limits of quantification, the qualifiers will be dropped and the numeric value used in the analysis (e.g., "< 3" will be summarized as "3" and "> 200" will be summarized as "200").

For all laboratory tests, results will be categorized as low, normal, or high based on their normal ranges. Results out of range will be identified as such on subject listings.

Using the safety population, shift tables using categories of low, normal, and high, comparing laboratory test results from baseline to each visit will be presented with percentages based on subjects with a non-missing value at baseline and post-baseline visit. For tests where the Common Terminology Criteria for

This document is confidential.

Adverse Events (CTCAE) criteria are available, shift tables will be based on the CTCAE grade. The CTCAE version 4.03 will be used for these summaries.

Analysis of allantoin will be done separately from other laboratory values.

